4.6 Biomarker Analysis

All continuous results of laboratory data will be converted to standard unit before any calculation if needed. Conversion of all lab values will be described in a separate document.

No statistical testing procedures will be applied to Biomarker analyses.

Absolute values as well as absolute change from baseline for the following biomarker data will be analyzed by visit using basic statistics:

- Li-Heparin blood collection tube (5-6 ml):
 - Plasma equilibrium angiotensin levels: Angiotensin II (Ang II), Angiotensin 1-7 (Ang 1-7), Angiotensin 1-5 (Ang 1-5), Angiotensin I (Ang I), Angiotensin 1-9 (Ang 1-9)
 - NT-proBNP, Ferritin
 - Aldosterone
 - Angiotensin-converting enzyme 2 (ACE2) activity and concentration
- EDTA blood collection tube (5-6 ml):
 - Plasma-Renin-Concentration (PRC)

- Cytokines: Interleukin 6 (IL-6), Interleukin 8 (IL-8), soluble tumor necrosis factor receptor type II (TNFR-II), Plasminogen activator inhibitor type-1 (PAI-1), von Willebrand factor (vWF-A2), Tumor necrosis factor- α (TNF- α)
- Alveolar epithelial markers: Soluble receptor for advanced glycation end products (RAGE), Surfactant protein-D (SP-D)
- Endothelial markers: Angiopoietin-2
- Immune function and COVID-19 antibodies: Immunoglobulin A (IgA), Immunoglobulin G (IgG) and Immunoglobulin M (IgM), Anti-SARS-CoV-2 antibody

Serology

The proportion of patients with positive or negative test results for HIV, Hepatitis B and Hepatitis C will be tabulated.

All serology data will be listed as well.

Clinical laboratory markers associated with poor outcome over time

Clinical laboratory markers associated with poor outcome (e.g., lymphocyte counts, D-Dimer, CRP) is a part of safety analysis (clinical laboratory assessments) and secondary endpoints. Absolute values as well as absolute change from baseline for this endpoint will be presented together with other clinical laboratory assessments.

4.7 Missing Values

No missing value imputation methods will be applied.

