⁴ Vital signs include temperature, heart rate, respiration, blood pressure, and oxygen saturation. Vital signs need to be tested before and after each dose (within 30 min before/after IMP administration).

⁵ physical examination could also be documented in the context of the general visit/health status assessment e.g. during a general clinical review

⁶ Pregnancy Test: for FOCP only

⁷ Laboratory tests include the following: in case a local lab cannot perform any of these parameters it should be reported as missing value

- Inflammatory indicators: C- reactive protein (CRP), erythrocyte sedimentation rate (ESR), and procalcitonin.
- Blood routines include: red blood cell (RBC) count, hematocrit (HCT) or hematocrit total, and classification of white blood cells (WBC), hemoglobin (Hb), platelet (PLT) count.
- Urine routine includes: glucose (GLU), pH (PH), urinary protein (PRO), red blood cells (BLD), and white blood cells (LEU).
- Stool routine + occult blood: red blood cells (BLD), white blood cells (LEU), occult blood.
- Blood biochemistry includes: aspartate aminotransferase (AST), alanine aminotransferase (ALT), alkaline phosphatase (AKP), total bilirubin (TBI), total protein (ALB), albumin (ALB), urea nitrogen (BUN), Creatinine (Cr), uric acid (UA), potassium (K), sodium (Na), eGFR (assessment is calculated according to the formula used in local laboratory).
- Myocardial enzymes: creatine kinase (CK) and isoenzyme (CKMB), lactate dehydrogenase (of LDH), [alpha] - hydroxybutyrate dehydrogenase ([alpha] - HBD), troponin (of cTnI).
- Coagulation functions include: prothrombin time (PT), activated partial thromboplastin time (APTT), D- dimer, FIB

⁸ results do not need to be available before randomization, results up to 4 weeks old are acceptable

⁹ 12- lead ECG: within 30 min after IMP administration

¹⁰ Respiration: blood gas analysis (oxygenation index, blood lactic acid) or pulse oximetry.

¹¹ Immune function: immunoglobulin (Ig A, Ig M, Ig G)

¹² Biomarkers comprising (per collection of whole blood 10-12 ml)

1 Li-Heparin blood collection tube (5-6 ml):

1. Plasma equilibrium angiotensin levels: Angiotensin II (Ang II), Angiotensin 1-7 (Ang. 1 -7), Angiotensin 1-5 (Ang 1-5), Angiotensin I (Ang I), Angiotensin 1-9 (Ang 1-9)
2. Aldosterone
3. ACE2 Activity and ACE2 concentration
4. Other exploratory RAAS Biomarkers indicators: specific exploratory indicators will be determined as needed

1 EDTA blood collection tube (5-6 ml):

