In the treatment period (day 1 to day 7) daily visits will be performed. If a patient will be discharged from hospital before day 7 treatment can be stopped at day of discharge. After seven days of treatment or early discharge before day 7 the follow-up (FU) period starts. Three FU visits (day 10, 14 and 28) will be conducted to assess efficacy and safety. The study assessments will be performed according to the study schedule (Table 1).

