8.7.1.2.4 Statistical Analysis

Continuous variables will be summarized with means, standard deviations, medians, lower and upper quartiles, minimums and maximums. Frequencies and percentages will be used to summarize categorical variables.

For time-to-event analyses censoring information will be used.

It is assumed that no patients will discontinue the study early prior to day 28 or hospital discharge in this Covid-19 setting. It is also assumed, that only very few missing values will arise due to not done evaluations. No imputation of missing values (e.g., no last observation carried forward (LOCF)) is planned, unless stated otherwise.

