2.2 Secondary Efficacy Endpoints

The following secondary efficacy parameters will be analyzed:

- Log transformed levels of lactate dehydrogenase (LDH) at Day 5 as a surrogate marker for organ damage (powered secondary endpoint)
- 28-day mortality (all cause death)
- Ventilator-free days (VFD) (up to 28 days or hospital discharge)
- Proportion of responders, defined as ≥ 2 improvement in WHO's 11-Point Score system at Day 7, 10, 14 and 28
- Time to death (all cause)
- Proportion of patients with any use of invasive mechanical ventilation (up to 28 days or hospital discharge)
- Time to first use of invasive mechanical ventilation (up to 28 days or hospital discharge)
- Absolute values and absolute change in PaO₂/FiO₂ ratio over time
- Absolute values and absolute change in modified Sequential organ failure assessment score (mSOFA score) over time
- Time to a 2-point decrease in WHO's 11-Point Score system
- Absolute values and absolute change in lymphocyte counts over time
- Absolute values and absolute change in C-reactive protein levels over time
- Absolute values and absolute change in D-dimer over time
- Absolute values and absolute change in log transformed levels of LDH over time
- Time to hospital discharge
- Change in viral RNA over time

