4.4.2 Analysis of Secondary Efficacy Endpoints

Log transformed levels of lactate dehydrogenase (LDH) at Day 5 as a surrogate marker for organ damage (powered secondary endpoint)

Results of LDH will be converted to standard unit before any calculation if needed. Conversion of all lab values will be described in a separate document 'Conversion_3570_VX-X_2020-MM-DD'. Standardized results will be log transformed for this endpoint.

Log transformed levels of LDH will be analyzed using linear regression adjusted for baseline log levels of LDH, center and age. 95% confidence intervals will be additionally calculated.

In protocol the wording of "minimization factors" is used: Stratification factors from the randomization are used in models as covariates.

Before application of the linear regression, it will be checked if the residuals are approximately normally distributed (QQ-Plot, Shapiro Wilk test). If there are no major violations of the normal distribution the model can be applied. If there are major violations available only descriptive analyses will be displayed.

Point estimate together with standard error and two-sided 95% confidence interval as well as p-value (two-sided) will be reported.

28-day mortality (all cause death)

The percentage of patients who have died at Day 28 will be presented by treatment group.

The following cases may occur:

- Patient discharged from hospital **and** discontinued before Day 28, will be followed up by telephone interview to check whether they are alive or dead, if unclear as no telephone interview available, death is assumed (worst case) at last available date of early termination, hospitalization or hospital discharge
- No discharge from hospital, **but** early discontinuation before Day 28 will be followed up by telephone interview to check whether they are alive or dead, if unclear as no telephone interview available, death is assumed (worst case) at date of early termination
- Discharged from hospital, **but** no discontinuation before Day 28: No telephone interview, but regular entry at Day 28 about alive/death status

Chi-squared test or Fisher's exact test

Proportion of responder, i.e. those patients that died, as well as the p-value (two-sided) will be reported.

Logistic regression

The following co-factors will be included in the logistic regression:

- ❑ Arterial hypertension
- ❑ Diabetes

- ❑ Coronary artery disease
- ❑ Age (<65 years vs. >=65 years)
- ❑ Center

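### Day 5 log LDH is analysed only in patients with a Day 5 sample, so early discharge and death would dilute a true benefit by an unknown amount; Day 2 and 3 LDH could reduce this

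*SAP*

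**What the plan says.** **Model.** SAP 4.4.2: "Log transformed levels of LDH will be analyzed using linear regression adjusted for baseline log levels of LDH, center and age". This is the only inferential analysis of LDH. Protocol 7.2.1 and SAP 2.2 label this endpoint, and no other secondary endpoint, as powered.

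**Missing data.** SAP 4.7: "No missing value imputation methods will be applied". Protocol 8.7.1.2.4: "No imputation of missing values (e.g., no last observation carried forward (LOCF)) is planned, unless stated otherwise". Nothing else is stated for LDH. The same protocol section gives two expectations: "It is assumed that no patients will discontinue the study early prior to day 28 or hospital discharge in this Covid-19 setting", and "It is also assumed, that only very few missing values will arise due to not done evaluations".

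**Who can lack a Day 5 value.** Protocol 8.1 allows early discharge: "If a patient will be discharged from hospital before day 7 treatment can be stopped at day of discharge". That sentence concerns treatment only. The sentences after it settle the sampling: follow-up begins at early discharge, and its visits are Days 10, 14 and 28. Footnotes 15 and 16 to Table 1 offer phone, home or outpatient contact for those follow-up visits, not for Day 5. Footnote 7 adds a second source of loss: "in case a local lab cannot perform any of these parameters it should be reported as missing value".

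**Other LDH data.** Table 1 schedules the laboratory panel, which contains LDH, at screening and on Days 1, 2, 3, 5, 7, 10, 14 and 28. SAP 4.4.2 uses the visits other than baseline and Day 5 only for summary statistics by visit.

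**Analysis set.** SAP 3.4 bases all efficacy analyses on the FAS, which is all randomized patients.

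**The concern.** The set actually analysed is the FAS minus everyone without a Day 5 sample. The plan treats LDH as a marker of organ damage, so patients who recover quickly plausibly leave with low values and patients who die early with high ones.

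If APN01 lowers LDH, it sends more low-LDH patients home before Day 5, and their values disappear from the APN01 arm. It also keeps alive some high-LDH patients who would have died on placebo, and their values stay in the APN01 arm. Both effects narrow the observed difference. Adjusting for baseline LDH removes only the part of this selection that baseline predicts. The course after randomisation is recorded in the Day 2 and Day 3 samples, which the model leaves out.

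The protocol's expectation of few missing values does not cover this. It concerns evaluations not done, and its assumption about discontinuation runs only up to discharge. For the mortality endpoints the SAP gives an explicit rule for unknown status. For Day 5 LDH it gives no estimand, no rule for death or discharge, and no sensitivity analysis.

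**Working it through.** **1. The plan's own figure.** The only sample-size calculation is for the primary endpoint (Protocol 8.7.2): 50% versus 30%, two-sided alpha 0.05, 80% power. With mean proportion 0.40 and pooled variance under the null,

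n per group = [1.960 × √(2 × 0.40 × 0.60) + 0.842 × √(0.50 × 0.50 + 0.30 × 0.70)]² / 0.20² = (1.358 + 0.571)² / 0.04 ≈ 93.

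This agrees with the stated 93 per group. No effect size, SD, sample size or loss rate is given for Day 5 LDH, so there is no LDH power figure to reproduce.

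**2. Simulation inputs (all assumed; none is in the documents).**
- Log LDH in SD units at Days 1, 2, 3 and 5, with correlation 0.85 per day of separation. Day 3 to Day 5 is then 0.85² = 0.72, and Day 1 to Day 5 is 0.85⁴ = 0.52.
- True effect −0.40 SD at Day 5, with a quarter of it present at Day 2 and half at Day 3.
- Leaving score = driving LDH value + normal noise (SD 0.7). The lowest scores are discharged and the highest die. Cut-offs are set to give the stated placebo rates.
- The driver is either Day 3 LDH (seen) or Day 5 LDH (unseen).
- 400,000 patients per scenario; center and age are not modelled.

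The planned analysis regresses Day 5 on arm and baseline in patients with a Day 5 value. The comparison fills Day 5 by arm from baseline, Day 2 and Day 3. It stands in for a repeated-measures model under missing at random.

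**3. Results.** Shrinkage = 1 − planned / full data.

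| Driver | Placebo discharge / death | Missing, placebo / APN01 | Full data | Planned | Shrinkage | Using Days 2 and 3 |
|---|---|---|---|---|---|---|
| Day 3 | 5% / 2% | 7.0% / 8.2% | −0.401 | −0.385 | 4% | −0.401 |
| Day 3 | 10% / 5% | 15.0% / 16.9% | −0.402 | −0.372 | 7% | −0.400 |
| Day 3 | 20% / 5% | 25.0% / 28.6% | −0.398 | −0.362 | 9% | −0.396 |
| Day 5 | 5% / 2% | 7.0% / 10.2% | −0.401 | −0.337 | 16% | −0.356 |
| Day 5 | 10% / 5% | 15.0% / 19.5% | −0.403 | −0.297 | 26% | −0.325 |
| Day 5 | 20% / 5% | 25.0% / 32.6% | −0.397 | −0.264 | 34% | −0.296 |

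When Day 3 drives leaving, using Days 2 and 3 removes the bias. When Day 5 does, it removes only part: in the first Day 5 row (0.356 − 0.337) / (0.401 − 0.337) = 30%, and in the last (0.296 − 0.264) / (0.397 − 0.264) = 24%.

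**4. No effect.** With the true effect set to 0, the bias was within 0.002 SD of zero in every scenario for both methods. In this set-up treatment affects leaving only through LDH.

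**5. Sensitivity to the assumptions.** Simulated trials of 200 patients, with log-LDH SD 0.45, true effect −0.20, Day 3 to Day 5 correlation 0.85 and leaving driven by Day 3, gave:
- one set of selection assumptions: −0.177 with 13% / 17% missing (placebo / APN01) and −0.167 with 25% / 31%. Shrinkage is 1 − 0.177 / 0.20 = 11.5% and 1 − 0.167 / 0.20 = 16.5%. Using Day 3 gave −0.199 and −0.200 with nearly the same standard error.
- milder selection: −0.197 with 3.5% / 4.5% missing and −0.184 with 30% / 35%. Shrinkage is 1.5% and 8%.

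Across the widest range of assumed inputs tried, shrinkage was about 0-18% with Day 3 driving leaving and about 4-35% with Day 5 driving it.

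**The case against.** The strongest reply is that the amount is unknown and may be trivial. Only losses before the Day 5 sample count, roughly Days 2 to 4. Patients enter with saturation at or below 93%, and the plan expects half the placebo arm to die or be ventilated, so few may go home that early. In the milder simulations the bias was 0.003 to 0.016 against a standard error of 0.05 to 0.06. This stands: no single percentage can be given for this trial.

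Second, the consequence is limited. Protocol 8.7.1.2.5 treats secondary variables as descriptive and exploratory, and the primary endpoint is unaffected. This stands.

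Third, a reader might infer that the plan discards the early LDH values and hides the losses. The documents do not support that. Log LDH and its change are tabulated at every visit, and SAP 4.1 reports discharges by visit and study discontinuation. What is absent is use of those values in the model and a breakdown of missing Day 5 LDH.

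Fourth, a repeated-measures model has its own faults. It implicitly assigns LDH values after death, it cannot help patients with no LDH after baseline, and it only partly corrects if leaving depends on unseen LDH. This stands and shapes the fix. The local-laboratory footnote belongs here too: a site that cannot run LDH on Day 5 probably cannot on Days 2 and 3, and that loss is not evidently linked to the patient's course.

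**Conclusion.** The gap is real. The design produces missing Day 5 values in patients selected by how they fared, the model drops them, and informative data already collected are left out of it. If APN01 lowers LDH, the planned estimate is diluted. The size cannot be read from the documents; the ranges above, about 0-18% and 4-35%, rest wholly on assumed loss rates, correlations and selection strength.

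Two stronger readings should be resisted. A reader might infer a risk of a false positive. The scenarios with no effect showed no bias, so the harm shown is a weakened true signal. That result assumes treatment affects leaving only through LDH. A reader might also take a mid-range figure such as 11-17% as the expected bias here. It is one part of a wide range, and the documents give nothing with which to choose a point in it.

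The change is worth making because it is cheap and the endpoint carries the powered label. It does not threaten the trial's main conclusion.

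**What to change.** 1. **Main analysis.** Fit a mixed model for repeated measures to log LDH on Days 2, 3 and 5, with treatment-by-visit, baseline log LDH-by-visit, age and center, and report the Day 5 contrast. Keep center, because the SAP adjusts for it and it is a randomisation factor. The model imputes nothing, so it is compatible with SAP 4.7.
2. **Sensitivity.** Keep the planned complete-case regression.
3. **Death.** State how death before Day 5 is handled, and add a sensitivity analysis for it, for example one that gives deaths the worst rank.
4. **Reporting.** Tabulate missing Day 5 LDH by arm and reason: discharge, death, laboratory unable to test, other.

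Record the change in SAP section 5 before unblinding. If unblinding has already happened, present the model as an added analysis and label it so.

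The cost is one extra model, one sensitivity analysis and one table, all on data already collected. The model assumes values are missing at random given earlier LDH, which is weaker than what the planned regression assumes but cannot be checked. The limits named under the objection remain: partial correction if unseen LDH drives leaving, no help for patients without LDH after baseline, and implied values after death unless item 3 is done.

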4.8 Data Base Closure and Blind Data Review Meeting (BDRM)

A data base closure will be performed prior to the analysis. All parameters will be checked, as specified in the data validation plan, and all queries resolved before data base closure and analysis.

A data review will be conducted prior to unblinding based on all data to check for protocol deviations and to allocate the patients to the analysis sets. At least the following items will be discussed:

- Informed consent procedure: ICF not or too late signed and dated by patient/investigator
- Violation of any in- or exclusion criterion
- Randomization procedure
- Incorrect use of IMP (storage, preparation and administration)
- Use of forbidden concomitant medication
- Delayed reporting of serious adverse events

These evaluations and assessments will be done together and in agreement with the Sponsor, however FGK in cooperation with CTC North will provide the Sponsor with the appropriate patient listings (as defined in Appendix A). Data review can be done via a telephone conference or in writing.

The affiliation of subjects to the SAF, FAS, and the PP set will be done prior to unblinding.

Data unblinding will be done after data base closure / data review. The unblinded data including formats will be provided from CTC North to FGK for final analysis.

4.9 Miscellaneous

For qualitative variables the frequencies (absolute and relative) are calculated. If no further remark is given in the description of the tables, following format will be used for all tables with qualitative variables (Note: In shift tables the percentages are based on the overall Total and not on the column Totals):

	Y-variable(s) (e.g., treatment group)					
	Category 1		Category 2		Total	
X-variable(s)	N	%	N	%	N	%
Category 1	xx	xx.x	xx	xx.x	xx	xx.x
Category 2	xx	xx.x	xx	xx.x	xx	xx.x
Missing	xx	xx.x	xx	xx.x	xx	xx.x
Total	xx	100.0	xx	100.0	xx	100.0

For this standard format the description of the tables in Appendix A determines only the X- and Y-variables. If another format of table is described in the details to the tables, the real design will be determined by the technical possibilities within SAS and may not look identical to the provided example. However, all information as displayed will be included.

Quantitative parameters will be described by declaring the mean value, standard deviation, minimum, first quartile, median, third quartile, and maximum. In the description of the tables this will be denoted by „basic statistics“. In general, minimum and maximum will be presented to the same level of precision as the raw data; means and medians, standard deviation, and quartiles will be presented to one further decimal place. P-values will be reported to four decimal places (i.e., 0.xxxx).

For frequency tables, all missing values (including user-defined missing values) will be combined in one category “missing” and included in the calculation of percentages. Percentages will be presented to one decimal place.

Tables and graphics will be presented only for scheduled visits.

The listings are always sorted by treatment group, center, and patient. If a different sorting order should be used for some listings this will be remarked separately. The variables for the special listings are explicitly given in the description of listings. All listings will be presented for the safety analysis set, if not stated differently, and indicator variables for further analysis sets, e.g., full analysis set, will be added if needed.

Enrolled but not treated patients (e.g. withdrawal before treatment) will be considered in tables and listings describing disposition of subjects, analysis sets as well as listings of PDs.

The following title will be used for all generated tables, listings, and graphs:

3570: APN01-01-COVID19 – final analysis

Page # of #

<Subtitle for description of contents - if applicable>

<Analysis set>

The numbering NNN of the tables/listings/graphs will be stated in the detailed description (Appendix A).

Following footnote will be used for all generated tables, listings, and graphs:

Date: <Actual date(ddmmmyyyy)>

Program: <Name of program>

All tables, listings, and graphs will be generated in A4 paper format.

The statistical evaluation will be performed using SAS version 9.4 or higher.

5 Changes from Protocol

In the following any changes on statistical aspects as described in the protocol are given:

- Wording of WHO's Proposed Core Outcome Measure Set for Clinical Studies of COVID-19 Infection for consistence (secondary endpoint):
 - Protocol: Time to a 2-point decrease in WHO scoring schema
 - SAP: Time to a to a 2-point decrease in WHO's 11-Point Score system
- Covariables used in statistical models and dynamic randomization
 - Protocol: Age as continuous variable
 - SAP: Age as dichotomous variable (<65 years vs. >= 65 years)

6 Signatures

Statistician:	
[name] FGK Clinical Research GmbH [name] [name] Germany	
11 Jan 2021 Date (ddmmmyyyy)	SN [Signature] Signature

Sponsor:	
[name] APEIRON Biologics AG [name]	
11 Jan 2021 Date (ddmmmyyyy)	[Signature] Signature
